#### **14.3.6 Analysis of exploratory endpoints**

##### **14.3.6.1 Analysis of exploratory efficacy endpoints**

Within-subject comparisons of lesion-specific binary endpoints (PaGA score of 0 or 1 at Week 6, and  $\geq 2$ -point reduction in PaGA score from baseline to Week 6) to assess treatment difference will be done by McNemar's test.

Within-subject comparisons of lesion-specific IGA, PaGA, scaling/hyperkeratosis, oedema/infiltration, dyspigmentation, scarring/atrophy, total skin disease damage score, and total skin lesion disease score to assess treatment difference at Week 6 will be done by a Wilcoxon signed rank test.

The PP analysis set will be the primary analysis set for exploratory endpoints. The analysis will be repeated for the FAS as a sensitivity analysis.

##### **14.3.6.2 Analysis of subject assessments**

The DLQI and PaGA scores will be summarised using descriptive statistics. The exploratory endpoints concerning PaGA will be analysed as described in Section 14.3.6.1.

The exit interviews will be reported separately (see Section 14.3.6.3).

### **14.3.6.3 Exit interviews**

The qualitative exit interviews will be audio-recorded, transcribed verbatim, and translated into English for analysis. Qualitative, thematic analysis methods will be used to analyse the verbatim transcripts. The results and analysis of the exit interviews will be reported separately from the CTR.

### **14.3.7 Analysis of pharmacodynamics and biomarkers**

The full results from the pharmacodynamics/biomarker analysis of all skin samples will be described separately in an addendum to the CTR. A summary of the results will be included in the CTR if available before finalisation of the CTR.

### **14.3.8 Exploratory analyses**

To assess the effect of delgocitinib cream compared with vehicle over time, within-subject comparisons of lesion-specific clearance according to IGA will be done by McNemar's test at baseline and at Weeks 2, 4, and 8. This analysis will be done on both the PP analysis set and the FAS.

### **14.3.9 Analysis of safety**

The analysis of safety will be based on the safety analysis set.

#### **14.3.9.1 Adverse events**

AEs will be coded during the trial according to Medical Dictionary for Regulatory Activities (MedDRA). AEs will be presented by preferred term and primary system organ class (SOC).

Treatment-emergent AEs will be summarised; however, all AEs recorded during the trial will be included in subject data listings. An event will be considered treatment-emergent if started after the first application of IMP, or if started before the first application of IMP and worsened in severity after first dose of IMP. The tabulations described in the following will only include the treatment-emergent events. In each of the tabulations, AEs are defined by MedDRA preferred terms within primary SOC.

An overall summary of the number of events and the number (percentage) of subjects with any treatment-emergent AEs, deaths, SAEs, premature discontinuations from the trial due to AEs, treatment-related AEs, and severe AEs will be presented.

The number of AEs and number of subjects with each type of AEs will be tabulated. The number of lesion-specific AEs will be tabulated by treatment. The number of lesions with lesion-specific AEs will be cross-tabulated within subject by treatment. The percentage of lesions with AEs will be compared between treatments by McNemar's test.

The severity for each type of AE will be tabulated. Where there are several recordings of severity for a given type of AE, severity will be taken as the most severe recording for that AE. The severity for each type of lesion-specific AE will be tabulated by treatment.

The causal relationship to IMP for each type of AE will be tabulated. Where the investigator has provided several causality assessments for a given type of AE, the information provided in the last AE report will be used for the final causality assessment. The rationale is that by the time the last AE report is completed, the investigator will be in possession of most information and should be able to provide their best causality assessment.

Related AEs are defined as AEs for which the investigator has not described the causal relationship to IMP as 'not related'. The number of related AEs and the number of subjects with each type of related AE will be tabulated. The number of lesion-specific, related AEs will be cross-tabulated within subject by treatment. The number of lesions with lesion-specific, related AEs will be tabulated by treatment. The percentage of lesions with related AEs will be compared between treatments by McNemar's test.

SAEs will be evaluated separately and a narrative for each will be given.

AESIs and AEs leading to withdrawal from trial or discontinuation of IMP will be listed.

#### **14.3.9.2 Vital signs**

The change in vital signs (blood pressure, peripheral pulse, body temperature) from baseline (Day 1) to Week 6 will be summarised as mean, standard deviation (SD), median, and minimum and maximum values.

#### **14.3.9.3 Clinical laboratory evaluation**

The change in each of the laboratory parameters from baseline (Day 1) to Week 6 will be summarised as mean, SD, median, and minimum and maximum values.

Laboratory parameters will be classified as 'low', 'normal', or 'high', depending on whether the value is below, within, or above the reference range. A shift table will be produced showing the categories at baseline (Day 1) against those at Week 6.

Subjects with laboratory parameters outside the reference range will be listed.

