| Skin lesion damage (dyspigmentation, scarring/atrophy)                       | X                      | X         | X      | X      | X      | X         |                            | X  |   | 11.3.3                        |
| Investigator assessments of safety                                    |                        |           |        |        |        |           |                            |  |   |                               |
| Vital signs (blood pressure, peripheral pulse, body temperature)             | X                      | X         |        |        | X      |           | X                          | X  |   | 11.4.1                        |
| Physical examination   | X                      |           |        |        | X      |           | X                          | X  |   | 11.4.2                        |
| ECG  | X                      |           |        |        |        |           | X                          |  |   | 11.4.3                        |
| Serology (central laboratory)  | X                      |           |        |        |        |           |                            |  |   | 11.4.4                        |

|   | Screening a | Treatment |        |        |                | Follow-up | Uns. visit (if applicable) | Early term. (if applicable) c | Primary endpoint visit (if applicable) d | References (protocol section) |
|---|------------------------|-----------|--------|--------|----------------|-----------|----------------------------|--|---|-------------------------------|
| Visit   | 1                      | 2         | 3      | 4      | 5              | 6         |                            |  |   |                               |
| Day/Week  | Day -28 to -7          | Day 1     | Week 2 | Week 4 | Week 6         | Week 8    | -                          | -  | Week 6  |                               |
| Visit window (days) b                | -28 to -7              | NA        | ±3     | ±3     | ±3             | ±3        | -                          | -  | ±3  |                               |
| Chemistry, haematology (central laboratory)     | X                      | X         |        |        | X              |           | X                          | X  |   | 11.4.4                        |

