| Urinalysis (central laboratory)                 | X j         | X         |        |        | X              |           | X                          | X  |   | 11.4.4                        |
| Urine pregnancy test                            | X                      | X         |        | X      | X              | X         | X                          | X  |   | 11.4.4                        |
| Adverse events                                  | X                      | X         | X      | X      | X              | X         | X                          | X  | X   | 13                            |
| Other assessments                        |                        |           |        |        |                |           |                            |  |   |                               |
| Size of target lesions                          | X                      | X         |        |        | X              |           |                            | X  |   | 11.6.2                        |
| Non-invasive skin sampling (patch) k |                        | X         | X      | X      | X              |           |                            | X  |   | 11.5.2                        |
| Skin biopsies (optional) l           |                        |           |        |        | X m |           |                            | X m, n                        |   | 11.5.3                        |
| Check of biopsy wound healing o      |                        |           |        |        |                | X         |                            |  |   | 11.5.3                        |
| Exit interviews l, p                 |                        |           |        |        | X              |           |                            | X  |   | 11.6.1.3                      |
| Photography l                        | X                      | X         | X      | X      | X m | X         |                            | X m                           |   | 11.6.3                        |
| End of trial form q                  |                        |           |        |        |                | X         |                            | X  | X   | 11.8                          |

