### 14.2 Trial analysis sets

All subjects screened in the trial will be accounted for in the CTR.

All randomised subjects will be included in the full analysis set (FAS). Exclusions from the FAS can be considered in special cases as described in ICH E9, Section 5.2.1 (Full Analysis Set). If it is decided to exclude a randomised subject from the FAS, a justification addressing ICH E9 will be given.

A per protocol (PP) analysis set will be defined by excluding subjects from the FAS who fulfil any of the following criteria:

- Receive no treatment with the IMPs.
- Do not complete the trial up to and including the Week 6 visit.
- Fail to provide efficacy data at the Week 6 visit.
- Are known to have used the wrong IMP on 1 or both target lesions.
- Do not fulfil the disease-defining inclusion criteria (that is, inclusion criteria no. 3-6).

Further exclusion of subjects or subject data will be decided upon after a blind review of the data, reviewing all the remaining in- and exclusion criteria, but focusing on concomitant medication that may affect DLE and also considering compliance and violations of visit windows.

A safety analysis set will be defined as all subjects who received IMP.

The decisions regarding inclusion/exclusion of subjects or subject data from the trial analysis sets will be documented in the analysis set definition document before breaking the randomisation code.

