#### **14.3.11 General principles**

All significance tests will be 2-sided using the 5% significance level. All tests will be interpreted exclusively in a descriptive manner, i.e. independently of other tests. All confidence intervals will be presented with 95% degree of confidence, unless otherwise specified.

An observed-cases approach will be used for tabulations of data by visit (that is, involving only those subjects who attended each specific visit).

Categorical data will be summarised using the number and percentage of subjects in each category. Lesion-specific categorical data will be summarised by cross-tabulation within subject by treatment. Continuous data will be summarised using the mean, median, SD, and minimum and maximum values.

All the analyses specified in the protocol will be reviewed in relation to the blinded data actually obtained, and the statistical analysis plan will be finalised before breaking the randomisation code.

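### Laboratory and vital-sign change summaries and the laboratory shift table use Day 1 and Week 6 only, so early termination and unscheduled values of subjects who stop early normally do not enter them

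*Combined protocol and SAP*

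**What the plan says.** Section 14.3.9.2 limits the vital-sign summary to change "from baseline (Day 1) to Week 6 will be summarised as mean, standard deviation (SD), median" and range. Section 14.3.9.3 sets the same interval for the change in each laboratory parameter. It then classifies values as low, normal or high against the reference range and adds: "A shift table will be produced showing the categories at baseline (Day 1) against those at Week 6". The section ends with a listing that carries no visit limit: "Subjects with laboratory parameters outside the reference range will be listed".

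Three general rules bear on this:

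- Section 14.3.11: "An observed-cases approach will be used for tabulations of data by visit".
- Section 14.3.12: missing values are not imputed.
- Sections 14.2 and 14.3.9: "A safety analysis set will be defined as all subjects who received IMP", and "The analysis of safety will be based on the safety analysis set".

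No rule in Section 14 assigns early termination or unscheduled values to Week 6. No end-of-treatment or worst-value summary is described.

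**The concern.** Safety is to be described on everyone who received the trial products, but these summaries can describe only those measured at Week 6. Those absent are subjects who stopped early, and some of them may have stopped for a safety reason under Section 10.2.1. Their values have usually been collected, because Section 10.3 asks them to attend an early termination visit that includes laboratory tests and vital signs.

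What is at stake is the completeness of descriptive safety reporting. Every subject receives both treatments (Section 9.3), so these are single-group tables that cannot separate delgocitinib from vehicle. No endpoint, test or sample size depends on them.

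**Working it through.** **Step 1. Where post-baseline values can come from.** The visits below are from Panel 2 in Section 4. The rows for chemistry and haematology, urinalysis, and vital signs have the same pattern.

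| Visit after Day 1 | Laboratory tests and vital signs taken? | Used in the change summaries and shift table? |
|---|---|---|
| Weeks 2 and 4 | No | – |
| Week 6 | Yes | Yes |
| Week 8 follow-up | No | – |
| Unscheduled | Yes | No |
| Early termination | Yes | No |
| Primary endpoint visit (early stoppers, Week 6) | No | – |

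A subject who stops treatment early and returns at Week 6 for the primary endpoint visit still has no Week 6 laboratory or vital-sign value. Early termination is then the only planned post-baseline measurement, with any unscheduled one in addition. With observed cases and no imputation, that subject drops out of the tables. This is what normally happens, not what always happens: an early termination visit inside the Week 6 window (±3 days) might be counted as Week 6, but no rule says so.

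**Step 2. An example.** Section 10.2.1 requires permanent discontinuation for ALT and/or AST above 3×ULN with total bilirubin above 2×ULN, or for confirmed ALT and/or AST above 5×ULN. No post-baseline laboratory test is scheduled during treatment before Week 6. Within the protocol, a post-baseline result that triggers this rule before Week 6 would therefore come from an unscheduled sample, which the shift table does not use.

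**Step 3. Size.** The inputs are from Section 14.1: 36 completing according to the protocol, 20% drop-out, 45 randomised.

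- Plan's own figure: 36 / (1 − 0.20) = 45. Reproduced.
- Drop-outs at the planned rate: 45 × 0.20 = 9.
- Coverage of the Week 6 tables if all 9 lack a Week 6 value: (45 − 9) / 45 = 36/45 = 80%. This also assumes that all 45 receive the trial products.
- Other drop-out rates (assumed): at 10%, 45 × 0.10 = 4.5; at 30%, 45 × 0.30 = 13.5.

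The 9 is the upper figure at the planned rate. The 20% allowance covers subjects who do not complete according to the protocol, and Section 14.2 also removes subjects from the per protocol set for using the wrong product or failing disease-defining criteria. Such subjects can attend Week 6 and have complete laboratory and vital-sign data.

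**Step 4. What could be recovered.** The documents give no attendance rate for early termination visits, so the shares below are assumptions. They apply to the upper case of 9 missing, with attendance at an early termination or unscheduled visit where the measurements are taken.

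| Share of the 9 with such a value (assumed) | Recovered | Coverage |
|---|---|---|
| 1/3 | 3 | 39/45 = 86.7% |
| 2/3 | 6 | 42/45 = 93.3% |
| All | 9 | 45/45 = 100% |

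**The case against.** The strongest reply is that little information is lost. The listing in Section 14.3.9.3 is not limited by visit, so any early termination or unscheduled laboratory value that would count as low or high is already shown by subject. The liver-enzyme example is always out of range and so always listed. Clinically significant new findings or deteriorations become adverse events (Sections 11.4.1 and 11.4.4.2), and events leading to discontinuation are listed (Section 14.3.9.1). Section 5.5 expects no systemic effects from treating at most about 1% of body surface area. The worst-value table would add only unscheduled samples beyond early termination. Those samples are taken selectively and include repeats of abnormal tests, so the table tilts towards abnormality with no comparator. Finally, Section 14.3.11 foresees a statistical analysis plan finalised before unblinding, where visit mapping could be settled.

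Most of this stands, and it limits the point to the summary tables. It does not remove the point. A listing of abnormal values gives neither the denominator nor the in-range changes of early stoppers, and no such listing is stated for vital signs. Low expected exposure lowers the likely yield but is no reason to leave collected values out of the summaries. A finalised plan could add a rule, but the text available here states the opposite one.

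Two stronger readings are tempting. A reader might infer that abnormal results in early stoppers would go unreported; the listing and the adverse event reporting contradict that. A reader might also infer that an early termination sample could set off the liver-enzyme stop. Panel 2 (footnote c) and Section 10.3 place that visit after the last dose, so it cannot.

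**Conclusion.** The point holds as a minor one. As written, Sections 14.3.9.2 and 14.3.9.3 leave out of the change summaries and the shift table the only post-baseline values planned for subjects who stop before Week 6. At the planned 20% drop-out this concerns at most about 9 of 45 subjects. That figure assumes that every drop-out lacks a Week 6 measurement; it falls if some attend Week 6 and leave only the per protocol set, and rises if actual drop-out exceeds 20%. It would be wrong to read 9 as an estimate of missing Week 6 values. The conclusion rests on the plan as set out in Section 14 and on the absence there of any rule mapping other visits to Week 6. It concerns completeness of description only, not efficacy conclusions or the comparison of treatments.

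**What to change.** Keep the Day 1 to Week 6 summaries and shift table, and add the following to the statistical analysis plan before unblinding:

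1. A change summary from baseline to end of treatment for laboratory values and vital signs, with end of treatment defined as Week 6 or, for subjects who stop earlier, the early termination visit.
2. One laboratory shift table from baseline category to worst post-baseline category, with lowest and highest shown separately, including early termination and unscheduled samples.

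The cost is some plan wording and a few extra descriptive tables, with no new visits, samples or subjects. There are two drawbacks. Early termination values come after varying times on treatment, and some are taken after the last dose. Unscheduled samples are selective and push the worst-value table towards abnormal categories. The new tables should therefore stand beside the Week 6 tables, not replace them.

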#### **14.3.10 Interim analysis**

No interim analysis is planned.

#### **14.3.11 General principles**

All significance tests will be 2-sided using the 5% significance level. All tests will be interpreted exclusively in a descriptive manner, i.e. independently of other tests. All confidence intervals will be presented with 95% degree of confidence, unless otherwise specified.

An observed-cases approach will be used for tabulations of data by visit (that is, involving only those subjects who attended each specific visit).

Categorical data will be summarised using the number and percentage of subjects in each category. Lesion-specific categorical data will be summarised by cross-tabulation within subject by treatment. Continuous data will be summarised using the mean, median, SD, and minimum and maximum values.

All the analyses specified in the protocol will be reviewed in relation to the blinded data actually obtained, and the statistical analysis plan will be finalised before breaking the randomisation code.

#### **14.3.12 Handling of missing values**

Missing values will be assumed missing at random and will not be imputed.

## **Appendix 1: Definitions of adverse events and serious adverse events**

### **Adverse event definition**

*An AE is defined as any untoward medical occurrence in a patient or clinical investigation subject administered a pharmaceutical product and which does not necessarily have a causal relationship with this treatment. An AE can therefore be any unfavourable and unintended sign (including an abnormal laboratory finding), symptom, or disease temporally associated with the use of a medicinal (investigational) product, whether or not related to the medicinal (investigational) product. (ICH Harmonised Tripartite Guideline for Good Clinical Practice, E6 (R1)).*

This definition includes:

- Accidental injuries.
- Events related to trial procedures.
- Reasons for any unfavourable and unplanned change in medication (drug and/or dose).
- Clinically significant worsening of pre-existing conditions.
- Reasons for admission to hospital or surgical procedures unless these were planned before the subject consented to trial participation.
- AEs commonly observed and AEs anticipated based on the pharmacological effect of the IMP.
- Any laboratory abnormality assessed as clinically significant by the investigator (see Section 11.4.4.2).

### **Serious adverse event definition**

An SAE is any untoward medical occurrence that

- Results in death.
- Is life-threatening.

- Requires in-patient hospitalisation or prolongation of existing hospitalisation. Planned hospitalisation or planned prolonged hospitalisation do not fulfil the criteria for being an SAE but should be documented in the subject's medical record.
- Results in persistent or significant disability/incapacity.
- Is a congenital anomaly/birth defect.

or

- Is a medically important condition. Events that may not be immediately life-threatening or result in death or hospitalisation but may jeopardise the subject or may require intervention to prevent one of the other outcomes listed in the definition above. Examples are intensive treatment in an emergency room or at home for allergic bronchospasm, blood dyscrasias and convulsions that do not result in hospitalisation, development of drug dependency or drug abuse.

